5.2. Baseline Definition

In general, Baseline will be defined for each subject as the last available, valid, non-missing assessment before the start of first study drug (ND0612) administration within the current study (ND0612H-012) or before the start of first study drug administration in study ND0612H-006 (for cohort 1). The analyses involving calculation of change from baseline will be based on the actual changes from baseline (not percentage), unless stated otherwise.

5.3. Significance level

Significance testing will be 2-sided using $\alpha = 0.05$. All p-values will be nominally described and no adjustment to multiple comparison will be performed.

5.4. Handling Withdrawals and Missing Data

In general, there will be no imputation for missing data, unless otherwise specified

The primary objective of this study is safety. Safety data will not be subject to any imputation and will be summarized on an observed case basis. For the analysis of the AEs, the incomplete follow-up will be taken into account by summarizing the data as annualized rates in addition to the

frequency counts and percentages. The analysis of the annualized rates takes into account the actual duration of the exposure to the study treatment.

For the efficacy endpoint, the missing data will be handled as follows:

- For patients who withdraw from the study, data at the early termination visit will be excluded from the by-visit summaries but will be included in the closest visit in case this visit was missing.
- For the continuous efficacy endpoints, likelihood-based modeling approach will be used to handle incomplete data. For this purpose, Mixed Model for Repeated Measures (MMRM) will be applied, see section 8.2.1.
- For categorical efficacy endpoints, the last non missing available data will be used for incomplete data.

All withdrawals will be included in all analyses up to the time of withdrawal. Subjects who are withdrawn prematurely from study drug and/or the study will be included in all analyses regardless of the duration of treatment.

5.5. Study Days and Visit Windows

Study days will be numbered relative to the first day of study drug administration. The start of treatment (day 1) is defined as the date on which a patient takes the first dose of study drug, as recorded in CRF. Days will be numbered relative to study start (ie, ..., -2, -1, 1, 2, ...; with day 1 being the start of study drug and day -1 being the day before the start of study drug).

The study data will be summarized as collected at the scheduled study visits regardless of visit window violations. For by-visit summaries, if there are multiple assessments at a post-baseline visit, then the last non-missing assessment at that visit will be used for the summary.

5.6. Pooling of Centers

The randomization (before Amendment 1) was stratified by region (Region 1 (Israel+USA) and Region 2 (Europe)). Because there was no randomization in this study after Amendment 1, the region is not included in the statistical models. As the center is not included as a factor in any of the statistical models, pooling of centers is not applicable.

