Randomization was performed in Cohort 2 before implementation of Protocol amendment 2 as follows. In order to ensure a balanced treatment allocation, subjects in Cohort 2 were to be randomized in a 1:1 ratio to receive either Regimen 1 or Regimen 2. A stratification by region was performed. IWRS assigned a unique randomization ID for each randomized subject and assigned subjects to a treatment regimen based on the pre-defined randomization schedule. Syneos Health biostatistics prepared the master randomization schedule, which was imported into the IWRS using a validated program.

Subjects who are withdrawn from the study and/or study treatment will not be replaced.

The Sponsor reserves the right to switch all subjects to one of the above 2 regimens, based on the results of the ND0612H-006 study. In this case, ongoing subjects will be switched at their next scheduled study visit and subjects not yet randomized will be allocated to the selected regimen instead of being randomized. Such a decision was taken on 08 December 2016, when Regimen 2 was discontinued.

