Regimen 2 (before Amendment 1), allocated to Regimen 1 (after Amendment 1, before Amendment 2) or allocated to Regimen 3 (after Amendment 2).

Treatment with the pump system will start at the clinic visit. Subjects will return to the clinic on the next day (Day 2) so that the study staff can observe them and adjust their oral anti-PD medications, if necessary. It is anticipated that subjects will down titrate their oral LD/DDI based on the investigator's clinical judgment. Subjects may be asked to perform additional unscheduled visits in cases where the investigator believes that additional titration is required to achieve stabilization. Subjects will remain on the assigned ND0612 dosing regimen for 12 months.

Subjects will receive a phone call at Day 4, and return for in-clinic visits at Week 1, and Months 1, 2, 3, 4, 6, 9, and 12.

For both cohorts: subjects will be allowed to continue with study treatment for an optional treatment extension period of 24 more months in which clinic visits will be performed every 3 months (Months 15, 18, 21 and 24, 27, 30,33 and 36) to assess subject safety.

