Following the approval of Protocol amendment 2 (dated 23 January 2017) all new subjects who were enrolled in Cohort 2 were assigned to treatment Regimen 3 (see dosing regimens for description of each regimen).

Unless stated otherwise, the subjects who received Regimen 2 and were switched to Regimen 1 during the study and will be included in the Regimen 1 group.

Figure 1: Cohorts and Regimen Changes following Protocol Amendments

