4.1. All screened subjects

This Analysis set consists of all patients who underwent screening and will be used for summary of disposition and data listings.

4.2. Intention-to-Treat (ITT):

The ITT set will include all subjects who were randomized (before Amendment 1) or enrolled (after Amendment 1) to the study. The subjects will be grouped according to the randomized (before Amendment 1) or allocated (after Amendment 1) treatment regimen.

4.3. Safety Set:

The Safety Set will consist of all subjects (cohort 1 and cohort 2) receiving at least 1 dose of study drug (ND0612). The subjects will be grouped according to the treatment regimen actually received. The Safety Set will be used for all summaries of safety and tolerability data.

4.4. Modified Intention-to-Treat (mITT) Set:

The mITT is a subset of the ITT analysis set. The mITT Set for cohort 2 will include subjects having ON/OFF Home diary data at baseline and at least one valid post-baseline measurement. The mITT Set for in cohort 1 will include subjects having UPDRS (part III) efficacy data at baseline and at least one valid post-baseline UPDRS (part III) measurement. The subjects will be grouped according to the randomized (before Amendment 1) or allocated (after Amendment 1) treatment regimen. The mITT Set will be used for all summaries and analyses of efficacy data.

Unless stated otherwise, the subjects who received Regimen 2 and were switched to Regimen 1 during the study will be included in the Regimen 1 group. However, sensitivity analyses will be conducted by excluding the subjects who were randomized to receive Regimen 2, as specified later in this SAP.

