8.2. Exploratory Efficacy Variable(s) and Analysis

8.2.1. Change in daily “ON” time without troublesome dyskinesia (“GOOD ON”) from Baseline to each visit

The changes from baseline to all post-baseline visits within each treatment regimen and the difference between the 2 treatment regimens in “GOOD ON” time (defined as the sum of "ON" time without dyskinesia and “ON” time with non-troublesome dyskinesia) will be estimated using a Mixed Model for Repeated Measures (MMRM). The model includes response data from all post-baseline visits with no imputation for missing data. The “GOOD ON” time at baseline will be included as a covariate and the treatment regimen (Regimen 1 or Regimen 3), visit (Month 1, 3, 6, 9 or 12) and the interaction between treatment regimen and visit will be included as fixed factors in the model. An unstructured covariance structure will be assumed and the denominator degrees of freedom will be computed using the Kenward-Roger method. In case the model will not converge

with the unstructured covariance structure, the heterogeneous compound symmetry (CSH) and the heterogeneous Toeplitz structure (TOEPH) will be used instead (in that order). Both the changes from baseline within each treatment regimen and the difference between the regimens will be estimated, separately for each visit, from the same MMRM using contrasts. Since ON/OFF diaries were assessed differently for Cohort 1, this cohort will be excluded from the model.

The changes in “GOOD ON” time will be estimated both as hours (normalized to 16 hours of awake time) and as a percentage out of awake time during the 24 hours of data collection. However, only one p-value will be provided due to the fact that the p-values will be identical.

The SAS code planned for the analysis is outlined below.

```
PROC MIXED DATA=DATA;  
CLASS TRTP AVISIT USUBJID;  
MODEL CHG=BASE TRTP AVISIT TRTP*AVISIT / SOLUTION DDFM=KR;  
REPEATED AVISIT / SUBJECT=USUBJID TYPE=UN;  
LSMEANS TRTP*AVISIT / PDIFF CL;  
WHERE AVISIT IN ('MONTH 1', 'MONTH 3', 'MONTH 6', 'MONTH 9', 'MONTH 12' ) AND COHORT=2;  
RUN;
```

8.2.2. Change in daily “OFF” time based on home "ON/OFF" diaries from Baseline to the 12-month visit

The daily “OFF” time will be analyzed similarly as the “GOOD ON” time replacing baseline “GOOD ON” time with baseline “OFF” time as covariate.

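### The end of randomisation does not justify leaving region out of the exploratory Regimen 1 versus Regimen 3 contrast; a region-adjusted estimate is a cheap, minor improvement

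*SAP*

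**What the plan says.** Protocol 8.4.5 describes the randomisation of Cohort 2 to Regimen 1 or Regimen 2 and notes that "A stratification by region was performed". SAP 5.6 gives the strata as Israel plus USA against Europe, and then leaves region out with a single reason: "Because there was no randomization in this study after Amendment 1, the region is not included in the statistical models".

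After Amendment 1, unrandomised Cohort 2 subjects went to Regimen 1. After Amendment 2, according to SAP 3.4, "all new subjects who were enrolled in Cohort 2 were assigned to treatment Regimen 3". SAP 4.4 places in the Regimen 1 group "the subjects who received Regimen 2 and were switched to Regimen 1 during the study".

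SAP 8.2.1 nevertheless plans a between-regimen comparison: "the difference between the regimens will be estimated, separately for each visit, from the same MMRM using contrasts". The model statement is "MODEL CHG=BASE TRTP AVISIT TRTP*AVISIT / SOLUTION DDFM=KR", so the only baseline covariate is the baseline value of the outcome. SAP 8.2.2 to 8.2.13 apply the same form to the other continuous efficacy endpoints.

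Region does appear elsewhere in the SAP. Section 6.3 summarises country and region by regimen, and section 4.5 lists region as a possible subgroup factor. Both group the USA against Europe plus Israel, which is not the grouping in 5.6. The subgroup model in 8.3 is fitted separately within each regimen.

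On status, SAP 5.3 sets two-sided 0.05 with nominal, unadjusted p-values. SAP 8.1 and Protocol 11.1.4.3.2 say that the regimens are not compared in a confirmatory way.

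**The concern.** A region term in a model can serve two purposes. One is to analyse as randomised, by carrying a stratification factor into the analysis. The other is to remove confounding when the groups were not formed by randomisation. Section 5.6 deals only with the first. For Regimen 1 versus Regimen 3 the second is the relevant one, because the two groups were enrolled in sequence under different amendments and nothing in the design keeps their regional mix alike.

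At stake is how the visit-by-visit difference between regimens, its confidence interval and its nominal p-value are read. If the regions contribute differently to the two periods and also respond differently, part of the reported difference is a difference between regions. The subgroup analysis cannot correct this, because a model fitted within one regimen contains no regimen contrast.

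**Working it through.** The plan gives no figure to reproduce. It has no power calculation, no regional shares by regimen, no region effect, no standard deviation of change and no Cohort 2 numbers by regimen. Everything below is illustration on assumed inputs.

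**Step 1: size of the bias.** Let p1 and p3 be the share of one region in Regimens 1 and 3, and g the difference between regions in mean change (hours). Without a region term, the contrast is biased by (p1 − p3) × g:

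| Mix difference | g = 0.5 h | g = 1.0 h | g = 1.5 h |
|---|---|---|---|
| 0 points | 0 | 0 | 0 |
| 20 points | 0.1 h | 0.2 h | 0.3 h |
| 40 points | 0.2 h | 0.4 h | 0.6 h |
| 60 points | 0.3 h | 0.6 h | 0.9 h |

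The bias is zero if either factor is zero.

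**Step 2: size against the standard error.** SE = s × √(1/n1 + 1/n3). With assumed n1 = 40, n3 = 120 and s = 3 h, SE = 3 × √(0.0250 + 0.0083) = 0.55 h. A bias of 0.4 h is then 0.73 SE.

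**Step 3: effect on the nominal 5% test when the regimens truly do not differ.** The rejection rate is 1 − Φ(1.96 − b/SE) + Φ(−1.96 − b/SE), where b is the bias. Six combinations were tried: group sizes 20/150, 40/120 and 60/110, each with s = 2.5 h and s = 3.5 h.

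- b = 0: 5.0% throughout.
- b = 0.3 h: 6.5% to 11.6%.
- b = 0.9 h: 19.1% to 61.1%.

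**Step 4: does a region term remove it, and at what price?** Each row is 5,000 simulated data sets from a single-visit linear model with 40 and 120 subjects, s = 3 h, no true regimen difference, and region as the only confounder:

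| Shares, Reg. 1 / Reg. 3 | g | Bias without region | Rejection without | Rejection with | SE without → with |
|---|---|---|---|---|---|
| 50% / 50% | 1.0 h | 0.00 h | 5.0% | 4.9% | 0.56 → 0.55 h |
| 70% / 50% | 1.0 h | 0.19 h | 6.1% | 4.7% | 0.55 → 0.55 h |
| 70% / 30% | 1.0 h | 0.41 h | 11.3% | 5.1% | 0.55 → 0.59 h |
| 80% / 20% | 1.5 h | 0.91 h | 36.7% | 5.5% | 0.56 → 0.67 h |

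With region in the model the bias was within 0.01 h of zero in every row. In the last row the SE rises by about 19% (0.669/0.563 = 1.19).

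**Step 5: weighting of the least-squares means.** In the third row the pooled share is (0.7 × 40 + 0.3 × 120)/160 = 64/160 = 40%. Averaging the two regions equally would describe a 50% mix and shift each within-regimen mean by 0.10 × 1.0 h = 0.1 h. The regimen difference itself does not move, provided the model has no region-by-regimen term.

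**The case against.** The strongest reply is about weight. The primary endpoint is safety and its analysis is descriptive. Protocol 11.1.4.3.1 describes the first efficacy endpoint as a within-group analysis, p-values are nominal, and the protocol's own model has no region term either. The stratum belonged to a Regimen 1 versus 2 randomisation that is no longer analysed as such, so there is no randomised contrast for a stratum term to honour. All of this stands, and it keeps the point minor.

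A second reply is that the SAP already shows the ingredients. Section 6.3 makes any imbalance in regional mix visible, and the subgroup analysis, if performed, shows whether region predicts change in ON time without troublesome dyskinesia. That also stands, but neither adjusts the contrast.

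A third reply is that one two-level term may reassure falsely. In Cohort 2, regimen follows the amendment period, so calendar period is completely confounded with regimen and a region term does nothing about it. This is correct and has to be stated wherever the adjusted result is reported.

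A reader might also infer that section 5.6 claims non-randomised comparisons need less adjustment, or that any regional difference in response passes into the contrast. The documents support neither. Section 5.6 explains only why a stratum was dropped. A regional difference enters the contrast only if regional mix also differs between regimens, and no section says that it does.

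**Conclusion.** The point holds as a minor one. The reason given in SAP 5.6 does not cover the contrast planned in SAP 8.2.1, and a factor already collected could remove one possible source of bias.

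The actual size is unknown. On the assumed ranges it is 0 to 0.9 h, and zero is a real possibility. The rejection rates depend further on assumed group sizes and standard deviations and on a simplified single-visit model, so they show direction and order of magnitude, not a prediction.

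It would go too far to read this as a flaw in the primary analysis, since the safety summaries use no such model. It would also go too far to treat a region-adjusted difference as a fair comparison of the regimens, because period confounding is untouched.

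**What to change.** 1. **Define region once.** SAP 5.6 groups Israel with the USA; SAP 4.5 and 6.3 group Israel with Europe. Settle one definition and use it throughout.
2. **Add region as a fixed factor to the 8.2.1 model**, at minimum as a sensitivity analysis, and carry it to the endpoints analysed in the same way. Because the contrasts are made by visit, consider region-by-visit as well (4 further degrees of freedom for five visits and two regions).
3. **Specify least-squares means at the observed regional mix**, so that within-regimen changes are not re-weighted to an artificial equal split of regions.
4. **Correct the rationale in 5.6.** Say that the stratum is no longer needed to reflect randomisation, and that region is included as a possible confounder of a non-randomised contrast.
5. **Label the result.** Report the regimen difference with its 95% CI as exploratory, non-randomised and non-concurrent, make no significance claim, and state that calendar-period confounding remains.

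The cost is a few lines of SAP text and code, with no new data. The statistical price is some precision if regional mix differs: in the illustrations the SE went from about 0.55–0.56 h to between 0.55 and 0.67 h.

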6. STUDY POPULATION

6.1. General

All Enrolled patients will be included in all study population summaries unless otherwise noted. Summaries will be presented by treatment group and overall unless otherwise noted.

6.2. Patient Disposition

The patient disposition will be summarized as follows and presented for each treatment regimen (Regimen 1 or Regimen 3) and overall, and for each cohort and overall. The percentages will be calculated from the ITT set, unless otherwise specified.

- The number of patients screened (i.e. the number of patients in the Screened Set)
- The number (%) of patients who failed screening (% calculated from the Screened Set), including the distribution of reasons for failing the screening
- The number of patients who enrolled to the study (i.e. the number of patients in the ITT Set)
- The number (%) of patients in the mITT and Safety sets
- The number of patients who were randomized (before Amendment 1), classified by the randomized dosing regimen (Regimen 1 or Regimen 2).
- The number of patients who received at least one dose of Regimen 2
- The number of patients who were switched from Regimen 2 to Regimen 1
- The number of patients who received at least one dose of Regimen 3
- The number (%) of patients who completed the 12-month treatment
- The number (%) of patients who discontinued the study prematurely including the distribution of reasons for premature discontinuations.

In addition, a CONSORT diagram will be provided.

6.3. Demographic and Other Baseline Characteristics

Demographics and baseline characteristics will be summarized descriptively for the ITT, mITT and Safety sets by treatment regimen and overall, and for each cohort and overall. In general, Baseline data for cohort 1 will be taken from 006 baseline visit while for cohort 2 baseline data will be taken from 012 baseline visit.

- Demographics: continuous: age, height, weight, Body Mass Index (BMI); categorical: age categorized as <65 years versus ≥ 65 years, BMI <20 vs BMI ≥ 20 , gender, race, country and region defined as Israel+Europe or USA (categorical)
 - The age will be calculated as the difference in days between the date of birth and date of screening and converted to years by dividing the number of days by 365.25. In case the exact birth day is missing, day 15 will be used. The BMI will be calculated as weight (kg) divided by squared height (m^2).
- PD history (time since diagnosis of PD, time since onset of motor fluctuations, time since onset of dyskinesia) will be summarized as continuous variables
 - The times will be calculated as differences in days between the date of diagnosis/onset and the date of screening. The missing diagnosis/onset day will be replaced by 15. In case the month is missing, it will be replaced by 6. The days will be converted to years by dividing the number of days by 365.25.
- Cognitive status: total score of Mini-Mental State Examination (MMSE), summarized as a distribution of values 30, 29, 28, 27, 26 and ≤ 25 . If baseline MMSE is not available in the current study, the baseline MMSE from study ND0612H-006 will be used instead
- Modified Hoehn and Yahr scale stage, summarized as categorical variable. If baseline Hoehn and Yahr scale stage is not available in the current study, the baseline Hoehn and Yahr scale stage from study ND0612H-006 will be used instead
- Baseline UPDRS scores: Sum of UPDRS Part I (Mentation, Behavior and Mood, items 1-4), Part II (Activities of Daily Living, items 5-17), Part III (Motor Examination, items 18-31), Part IVA (Dyskinesia sum score, items 32-35) and Part IVB (Fluctuation sum score, items 36-39)
 - Each sum score will be calculated as the sum of the individual items. Missing individual items will not be imputed. If there is at least 1 missing item, the corresponding sum score will be set as missing

- Baseline ON time without troublesome dyskinesia determined by “ON/OFF” diary (defined as the sum of ON time without dyskinesia and ON time with non-troublesome dyskinesia)
 - For derivation, see section 3.2.3

- Baseline “OFF” time as determined by “ON/OFF” diary (continuous)
 - For derivation of the “OFF” time, see section 3.2.3

- Baseline ON time without dyskinesia as determined by “ON/OFF” diary (continuous)
 - For derivation, see section 3.2.3.

- Baseline ON time with Troublesome dyskinesia as determined by “ON/OFF” diary (continuous)

- Total daily levodopa dose as IR levodopa equivalent dose (continuous); total administered daily levodopa dose (without conversion); total administered daily levodopa dose (without conversion) categorized as <400 mg or ≥400 mg.); daily levodopa dosing frequency (categorical); patients using COMT inhibitors, patients using carbidopa or benserazide as DDI. For conversion factors, see Table 1.

Table 1 - IR levodopa Equivalent Dose Conversion Factors

Previous medication	LD Conversion factor
LD+Opicapone	×1.4
LD+Entacapone	×1.33
LD+Tolcapone	×1.5
Stalevo	×1.33
Benserazide Methyldopa: Aldomet, Aldoril, Dopamet, Dopegyt DL-x-Difluoromethyl DOPA (DFMD) 3',4',5,7-Tetrahydroxy-8-methoxyisoflavone	×1
Controlled-release (CR) or Extended release (ER) Levodopa (e.g. Rytary, Numient)	×0.7

6.4. Medical History and Concomitant Diseases

Medical history data will be coded using the Medical Dictionary for Regulatory Activities (MedDRA). The medical history data will be summarized with frequencies and percentages of patients with at least one medical history item, and patient frequencies and percentages on the System Organ Class (SOC) and Preferred Term (PT) levels. The number of events will also be summarized. The table will be sorted by overall descending frequency of SOC and then, within a SOC, by overall descending frequency of PT. The summary of medical history data will be done for the Safety set broken down by treatment group.

